#### **8.1.1.2 Tumor scans during the study**

The first on-study scan assessment should be performed at 6 weeks ( $\pm 2$  weeks; starting from cycle 1 day 1). Subsequent tumor scans should be performed every 6 weeks ( $\pm 2$  weeks) or more frequently if clinically indicated. Scan timing should follow calendar days and should not be adjusted for delays in cycle starts.

All supplemental imaging must be collected.

Objective response should be confirmed by repeat scan performed at least 4 weeks after the first indication of a response is observed. Patients will then return to the regular scan scheduled, starting with the next scheduled time point. Patients who receive additional scans for confirmation do not need to undergo the next scheduled scan if it is fewer than 4 weeks later; scans may resume at the subsequent scheduled time point.

When radiological disease progression is identified by the investigator in clinically stable patients, disease progression is to be confirmed by another set of scans performed 4 to 8 weeks later, per iRECIST guidelines in section [8.1.1.5](#).

If disease progression is not confirmed, clinically stable patients are to continue study interventions until progression is confirmed. Patients are to return to their regular scan schedule. If the next scheduled scan will occur in less than 4 weeks, this scheduled scan may be skipped.

If disease progression is confirmed, study interventions will be discontinued. Exceptions are detailed in section [8.1.1.5](#).

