### 9.3 Statistical analyses

#### 9.3.1 General considerations

Analyses will be descriptive (i.e., without a comparison). Efficacy analyses will be performed for each indication separately. Safety will be analyzed as described in section [9.3.3](#).

Summary statistics will include:

- Counts and percentages (categorical data)
- Number of observations, mean, standard deviation, median, minimum, and maximum (continuous data)

The ORR, iORR, BOR, iBOR, CBR, iCBR, CTC response, and PSA response will use the exact method based on the binomial distribution[56](#) to derive 95% confidence intervals (CIs).

---

Kaplan-Meier estimations and estimations of median (if reached) with log-log 95% CI, Q1 (25th percentile), and Q3 (75th percentile) will be used for time to confirmed PSA progression (mCRPC only), DoR, iDoR, PFS, iPFS, TtR, iTtR, and OS. In case of a confirmed response or disease progression, the date of the first tumor assessment or PSA evaluated as response or progression will be used for the time-to-event variables.

Depending on the amount of missing data, a sensitivity analysis will be performed for time-to-event endpoints. If such an analysis is planned, it will be described in the final Statistical Analysis Plan (SAP).

The last value of PSA, CTC count, CT scan, bone scan, or MRI on or up to 28 days before the date of the first study treatment will be used as the baseline value for each assessment. Only tumor assessments prior to or at the date of initiation of further-line therapy and using CT scan, bone scan, or MRI will be used for the evaluation of tumor response.

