### 9.3.3.2 Efficacy endpoints

- iORR

The iORR is defined as the proportion of patients with complete response (iCR) or partial response (iPR) and will be analyzed and presented as a point estimate and a 95% CI for each indication separately. Patients with missing data will be considered as non-responders.

- BOR and iBOR

The BOR and iBOR are defined as the best response from the start of study treatment until progression of disease or death and will be summarized with counts and percentages together with a 95% CI for each indication separately. Stable disease (SD, iSD) needs to last at least 6 weeks from the baseline scan; if not, at least one follow-up scan is required to declare stable disease.

- DoR and iDoR

The DoR and iDoR are defined as the time until progression of disease for patients with partial response (PR, iPR) or complete response (CR, iCR) and will be summarized using Kaplan-Meier estimates for each indication separately. Responders will be considered to have an ongoing response if they: i) have not progressed, and ii) have not started a new anti-cancer therapy, and iii) have not been lost to follow-up, and iv) are alive.

Patients with missing data will be censored/considered as having an event as specified below:

Situation	Date of progression or censoring	Outcome
No progression, no death. No start of new anti-cancer therapy.	Date of the last evaluable tumor assessment.	Censored
No progression, no death. Start of new anti-cancer therapy.	Date of the last tumor assessment with non-progression before the start of new anti-cancer therapy.	Censored
Progression or death after one missed adequate tumor assessment.	Date of progression or death, whichever is earliest (if both occur).	Progressed
Progression or death after more than one missed adequate tumor assessment.	Date of the last evaluable tumor assessment.	Censored

- CBR and iCBR

The CBR and iCBR are defined as the number of partial responses (PR, iPR), complete responses (CR, iCR), and stable diseases (SD, iSD) and will be analyzed and presented as a point estimate and a 95% CI for each indication separately. Stable disease (SD, iSD) needs to last at least 6 weeks from the baseline scan; if not, at least one follow-up scan is required to declare stable disease. Patients with missing data will be considered as non-responders.

- PFS and iPFS

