10.13.3 Best Overall Response (BOR and iBOR)

Per RECIST (v 1.1): The best overall response (BOR) according to RECIST v 1.1 will be programmatically derived from the first dose date until the first documented disease progression, death, or start of new anti-cancer therapy. BOR will be determined according to the following rules in a stepwise manner for subjects with measurable disease:

Step	Condition
Step 1: BOR of CR If a BOR of CR is not determined, Step 2 will be performed.	At least two consecutive determinations of CR more than 4 weeks apart, or if not consecutive, with no other assessment between the two determinations other than unable to evaluate (NE), CR.
Step 2: BOR of PR If a BOR of PR is not determined, Step 3 will be performed.	At least two consecutive determinations of PR or CR, more than 4 weeks apart, or if not consecutive, with no other assessment between the two determinations other than NE, CR, PR.
Step 3: BOR of SD If a BOR of SD is not determined, Step 4 will be performed.	At least one SD assessment (or better), ≥ 6 weeks (≥ 42 days) after start of study treatment; if not, at least one follow-up scan (i.e., consecutive scan) evaluated as SD (or better) is required to determine a BOR of SD. If not consecutive scans, with no other assessment between the two determinations other than NE, CR, PR, SD.
Step 4: BOR of PD If a BOR of PD is not determined, Step 5 will be performed.	At least one (i.e., any) PD after baseline.

Step	Condition
Step 5: BOR of NED If a BOR of NED is not determined, Step 6 will be performed.	If no measurable disease at baseline and all subsequent assessments will be NED.
Step 6: BOR of NE	Measurable disease at baseline, but not all or any target lesions have been evaluated, or if derivation of BOR from Step 1 to 5 does not apply.

Based on the table above, the following examples cover the possibilities for best overall response considering the first tumor assessment as response (CR, PR), and subsequent or consecutive tumor assessments:

Overall response First time point	Overall response Subsequent time point	BEST overall response
CR	CR	CR
CR	PR	SD, or PR**
CR	SD	SD
CR	PD	SD*, or PD
CR	NE	SD*, or NE
PR	CR	PR
PR	PR	PR
PR	SD	SD
PR	PD	SD*, or PD
PR	NE	SD*, or NE

* Provided minimum criteria for SD duration is met

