12.7.9 PSA Response

The PSA response will be summarized using descriptive statistics (frequency and percentage) together with a 95% CI for the mCRPC indication cohort.

Responses will need confirmation by a second consecutive value obtained 4 or more weeks after the first value indicated a response. Evaluable patients with no confirmed response as defined above will be classified as non-responders.

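### SAP 10.13.3 departs from the protocol on the response-confirmation interval and the stable-disease anchor without listing either in SAP 6.1, and its Step 2 contradicts its own CR-then-PR example

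*SAP*

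**What the plan says.** **Confirmation of response.** Protocol 8.1.1.2: "Objective response should be confirmed by repeat scan performed at least 4 weeks after the first indication of a response is observed". The same section lets a site drop a scan afterwards: "Patients who receive additional scans for confirmation do not need to undergo the next scheduled scan if it is fewer than 4 weeks later". The ORR definition in protocol 9.3.2 gives no interval. SAP 10.13.3, Step 2, asks for "At least two consecutive determinations of PR or CR, more than 4 weeks apart". Step 1 sets the same interval for CR, and the PCWG3-modified and iRECIST tables repeat it. For PSA, SAP 12.7.9 says: "Responses will need confirmation by a second consecutive value obtained 4 or more weeks after the first value indicated a response".

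**Stable disease.** Under protocol 9.3.3.2, SD "needs to last at least 6 weeks from the baseline scan"; failing that, one follow-up scan is needed. Under protocol 9.3.1, the last scan "on or up to 28 days before the date of the first study treatment will be used as the baseline value". SAP Step 3 instead wants an SD-or-better scan 42 days or more "after start of study treatment; if not, at least one follow-up scan (i.e., consecutive scan) evaluated as SD (or better) is required". All three SAP tables use this anchor.

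**CR followed by PR.** SAP 10.13.3 states: "BOR will be determined according to the following rules in a stepwise manner for subjects with measurable disease". Step 2 accepts any two consecutive PR or CR determinations, with no condition on order. The example table, presented as following from the steps, gives SD for CR then PR, or PR subject to a footnote. The footnote allows PR when the first CR is re-entered as PR in the eCRF. Otherwise the result is SD. It states that this holds for RECIST 1.1 and iRECIST.

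**Dependence.** ORR is the share of patients with a BOR of CR or PR (SAP 10.13.4). Clinical benefit rate (CBR) adds SD (SAP 10.13.7). SAP 6.1, the list of changes from the protocol, mentions neither the interval nor the SD anchor.

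**The concern.** BOR is to be derived by program, and the primary endpoint is read straight from it, so the wording of each step decides who counts as a responder. A programmer following the SAP rejects a confirmation at exactly 28 days that the protocol accepts. For CR then PR, one programmer coding Step 2 as written and another coding the footnote would report different ORRs from the same data.

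The SD anchor matters for the secondary endpoints: the same scan can make a patient SD under the protocol and PD under the SAP. Departures from a protocol definition belong in SAP 6.1. That section does declare a change of this small kind for the circulating tumor cell count, where the cut-off moves from above 5 to 5 or above. Its silence here leaves a reader unable to tell an intended change from a slip.

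**Working it through.** Days are counted from first dose. SAP 10.17 sets 1 week = 7 days, so 4 weeks = 28 days and 6 weeks = 42 days. Scans are due every 6 weeks, plus or minus 2 weeks (protocol 8.1.1.2). The first on-study scan may therefore fall on days 28 to 56 and the second on days 70 to 98. The baseline scan may be 0 to 28 days before dosing (protocol 9.3.1).

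As a base check, Steps 1 to 4 and the not-evaluable fallback were coded literally and run on the ten pairs in the SAP's example table. Nine rows reproduce. The one that fails is CR then PR.

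**1. Confirmation interval**

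| Scans | SAP (gap > 28) | Protocol (gap ≥ 28) |
|---|---|---|
| PR, PR 27 days later, then PD | SD | SD |
| PR, PR 28 days later, then PD | SD | PR |
| PR, PR 29 days later, then PD | PR | PR |
| PR day 42, PR day 70, day-84 scan skipped, PD day 126 | SD | PR |
| PR day 42, PR day 70, PR day 84, PD day 126 | PR | PR |

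Only the exact 28-day gap separates the rules, and a later confirming scan removes the difference (84 − 42 = 42 days). The skip rule makes the fourth row possible, because day 84 is 14 days after day 70, fewer than 28.

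For illustration, suppose two successive scheduled scans each fall uniformly and independently in their windows. A gap of 28 needs the first scan on days 42 to 56, which is 15 of 29 × 29 = 841 pairs, or 1.8%. That is before requiring a response and no later confirmation. It does not describe extra scans booked specifically for confirmation.

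**2. SD anchor**

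Let *d* be the day of the first on-study scan and *b* the days from baseline scan to first dose. With SD at *d* and no second SD-or-better scan, the protocol gives SD if *d* + *b* ≥ 42 and the SAP gives SD if *d* ≥ 42. They differ when *d* < 42 ≤ *d* + *b*. Example: SD on day 35, PD on day 77, *b* = 14. Then 35 + 14 = 49 ≥ 42, so SD under the protocol; 35 < 42, so PD under the SAP.

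For illustration, count day combinations under uniform timing:
- All allowed values: *d* = 28 admits *b* = 14 to 28 (15 values), rising to 28 values at *d* = 41. The sum 15 + … + 28 = 301, and 301/841 = 35.8%.
- Excluding a baseline scan on the dosing day: 301/812 = 37.1%.
- Baseline scan within 7 days of dosing: 28/232 = 12.1%.
- All first scans on day 42 or later: 0%.

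**3. CR then PR**

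Take CR on day 42, PR on day 84, PD on day 126. The gap is 42 days, so Step 1 fails (only one CR) and Step 2 is met: PR. The footnote gives SD unless the eCRF entry is corrected.

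**Size per reclassified patient:** 100/N points.

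| N | Points |
|---|---|
| 57 (colorectal, cSCC) | 1.75 |
| 55 (hepatocellular) | 1.82 |
| 51 (mCRPC) | 1.96 |
| 50 (NSCLC, ovarian) | 2.00 |
| 35 (mCRPC minimum with measurable disease, protocol 5.1) | 2.86 |

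SAP 6.1 records that recruitment stopped after the August 2023 futility analysis, so final cohorts may be smaller. At the futility sample sizes, used only as an illustration, the shift runs from 100/35 = 2.9 to 100/12 = 8.3 points.

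**The case against.** The strongest reply is that little turns on any of this. The protocol's interval sits in the imaging section and tells sites when to rescan, while its ORR definition gives none. The gap rule bites on one day only, and a patient still responding at the next scan is confirmed under both texts. The PSA rule concerns another endpoint and does not show which tumor rule was meant. The SAP keeps the protocol's six weeks and its follow-up-scan fallback for SD. The footnote already answers CR then PR, and a specific rule for a named sequence is naturally read as qualifying a general one. At the futility analysis, responses with a confirmatory scan still pending are counted anyway (SAP 11.0).

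Most of that stands, and it sets the severity. It does not remove the differences. Protocol 8.1.1.2 is the only place where the protocol gives a tumor-response confirmation interval, so the SAP departs from the only rule there is. The footnote settles intent, but Step 2 neither cites it nor excludes the sequence, and Step 2 is what will be programmed.

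Three stronger readings are tempting:
- **That about a third of patients would be misclassified on SD.** The 35.8% is a share of calendar-day combinations under assumed uniform timing, conditional on no second SD-or-better scan. The documents give neither the timing nor that frequency.
- **That the classification of CR then PR is open, so either outcome may be chosen.** The footnote already states the outcome. The trial is open-label and response data were reviewed at futility, so a free choice now would be made after seeing data.
- **That SAP 10.13.9 adds a further conflict** by dating a response from a first PR or CR confirmed by a later PR or CR. That wording can be read as dating a response already confirmed under 10.13.3, and it shows no error.

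**Conclusion.** The point holds, as a minor one. SAP 10.13.3 makes two undeclared departures from the protocol and contains one internal contradiction.

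- The confirmation interval can change BOR and ORR (and iBOR and iORR), only at a gap of exactly 28 days with no later confirming CR or PR.
- The SD anchor can change BOR and CBR (and iBOR and iCBR), never ORR, and only without a second SD-or-better scan.
- CR then PR more than 4 weeks apart can change ORR, depending on whether Step 2 or the footnote is coded.

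The number of patients affected cannot be derived from the documents. The per-patient shifts at planned sizes are lower bounds if the final cohorts are smaller. It would go too far to infer that the trial's conclusions are at risk: protocol 9.1 and SAP 12.0 plan no hypothesis test, so the effect is on reported proportions and their confidence intervals.

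**What to change.** Make these changes before database lock, and without reference to which patients they reclassify:

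1. In Steps 1 and 2 of all three tables in SAP 10.13.3, set the interval to at least 4 weeks (≥28 days).
2. In Step 3 of all three tables, time SD from the baseline scan as in protocol 9.3.3.2. If the first-dose anchor is intended, keep it, and list and justify the change in SAP 6.1.
3. Carry the existing footnote into Step 2: CR then PR counts as PR only if the first CR has been corrected to PR in the eCRF, and otherwise as SD.

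The cost is SAP wording and a few lines of code, with no new data.

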10.13.4 Objective Response Rate (ORR and iORR)

- Per RECIST (v1.1): The ORR is the proportion of patients who achieved BOR of CR or PR.
- Per iRECIST: The iORR is defined as the proportion of patients who achieved iBOR of iCR or iPR.

10.13.5 Tumor Burden

Change in Tumor burden will be calculated as the percent CFB in target lesions per time point. Per RECIST criteria this will only be done for target lesions defined at baseline.

It will be derived as:

- $((\text{Sum of target lesions at post-baseline assessment} - \text{sum of target lesions at baseline}) / \text{sum of target lesions at baseline}) \times 100$

The absolute maximum reduction in target lesions from baseline will be derived across all the post-baseline assessments until documented disease progression or start of new anti-cancer therapy, whichever is earliest.

10.13.6 Duration of Response (DOR and iDOR)

- Per RECIST (v1.1): Duration of response is defined as the time from first documentation of overall response leading to a confirmed CR or PR until the time of first documentation of overall response of disease progression (PD) or death.
- Per iRECIST: Duration of response is defined as the time from first documentation of overall response leading to a confirmed iCR or iPR until the time of disease progression or death. The date of disease progression will be the first instance of iUPD that is confirmed by a later iCPD, this can occur on the subsequent assessment or after a series of persistent iUPD assessments. The date of iUPD will also be used as disease progression if the iUPD assessment is followed by:
 - if the patient stops protocol treatment because they were judged to be clinically unstable, or
 - no further tumor assessments are done, or
 - the next timepoint responses are all iUPD, and iCPD never occurs , or
 - if the patient dies from their cancer.

An iUPD assessment followed by subsequent non-PD assessments will not be considered as the start of progression. Stopping protocol treatment due to clinical instability is identified as subjects discontinuing from SOT101 with reason 'clinical progression'.

- Per PCWG3-modified RECIST 1.1: Duration of response is defined as the time from first documentation of overall response leading to a confirmed CR or PR until the time of first documentation of overall response of (confirmed) disease progression (PD) or death.

Clinical deterioration alone will not be considered as documented disease progression. Only tumor assessments performed before or on the start of any new anti-cancer treatment (including radiation therapy to the tumor lesion (s)) will be considered in the assessment of DOR and iDOR.

10.13.7 Clinical Benefit Rate (CBR and iCBR)

- Per RECIST (v1.1): The CBR is the proportion of patients who achieved BOR of CR, PR, or SD.
- Per iRECIST: The iCBR is defined as the proportion of patients who achieved iBOR of iCR, iPR or iSD.
- Per PCWG3-modified RECIST (v1.1):
 - Patients with measurable disease: as per RECIST 1.1
 - Patients with measurable and non-measurable disease: The CBR is the proportion of patients who achieved BOR of CR, PR, SD, Non-CR/Non-PD, NED.

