#### Disease characteristics

4. Patients with the following histologically or cytologically confirmed solid tumor indications and line of treatment:
  - NSCLC
    - For the second-line or third-line treatment of patients with advanced and/or metastatic NSCLC with disease progression on or after an immune checkpoint inhibitor-containing regimen and a platinum-containing regimen, with no EGFR or ALK genomic tumor aberrations, and who are not amenable to curative treatment
  - Colorectal cancer
    - For the first-line treatment of patients with unresectable or metastatic MSI-H/dMMR colorectal cancer
  - cSCC
    - For the first-line treatment of patients with recurrent or metastatic cSCC or second line if refractory or relapsed after an immune checkpoint inhibitor-containing regimen, and in whom radiotherapy is not feasible (based on data from study SC103 [AURELIO-03])
  - Advanced hepatocellular carcinoma (not applicable in France)
    - For the second- to fourth-line treatment of patients with advanced hepatocellular carcinoma having progressed on or after a checkpoint inhibitor-containing regimen
  - mCRPC
    - For the second- to fifth-line treatment of patients with mCRPC after recurrence or failure of docetaxel and prior treatment with abiraterone, enzalutamide, or any other androgen receptor-targeted agent
  - Ovarian cancer
    - For the second- to fifth-line treatment of patients with advanced ovarian cancer after recurrence or failure on the last platinum-based therapy within 6 months
5. Have measurable disease per RECIST 1.1 as assessed by the local site investigator/radiology; lesions situated in a previously irradiated area are considered measurable if progression has been demonstrated in such lesions

mCRPC: Patients with both measurable and non-measurable disease will be enrolled. At least 35 patients with measurable disease will be enrolled. Patients with no measurable disease and only widespread bone disease must have a CTC count of  $\geq 5$  cells per 7.5 mL of blood.

6. Availability of tumor tissue from a fresh biopsy at screening unless the biopsy cannot be obtained due to safety reasons or non-accessibility of the tumor site. If it is not possible to obtain a fresh biopsy, every effort should be taken to retrieve an archival biopsy. Archived, fixed tumor tissue may only be collected if taken preferentially after completion of the most recent systemic tumor therapy and within 12 months prior to the first dose of study treatment.

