6.1 Changes from Protocol

The following changes to the protocol have been applied:

Endpoint of “Circulating tumor cell (CTC) count conversion from >5 to <5 cells per 7.5 mL of blood” for metastatic castration-resistant prostate cancer (mCRPC) only will be analyzed as a conversion from ≥ 5 to <5 cells per 7.5 mL of blood.

Endpoint of “Confirmed PSA decline of $\geq 50\%$ ” will not only evaluate the response at 6 months post-trial entry: all timepoints will be considered as per the schedule of assessments (Section 1.3.3 of Study Protocol).

Additional sensitivity analyses and exploratory endpoints:

As a sensitivity analysis for Best Overall Response (BOR) as per RECIST 1.1: BOR will also be performed as per Prostate Cancer Clinical Trials Working Group 3 (PCWG3)-modified RECIST 1.1 to study the effect of progressive disease in bone on the BOR, for patients with mCRPC.

As a sensitivity analysis to Clinical Benefit Rate (CBR) as per RECIST 1.1: CBR will also be performed for all patients in mCRPC – with both measurable and non-measurable disease – as per PCWG3-modified RECIST 1.1, to study the effect of progressive disease in bone on the CBR.

Other sensitivity analyses using All Subjects as Treated (ASaT) population on selected efficacy endpoints.

As per the EMA guideline on the evaluation of anticancer medicinal products in man, the endpoint PFS2 has been added as an exploratory endpoint.

Following Futility Analysis in August 2023, recruitment to the study was stopped. Exploratory Endpoints will no longer be analyzed.

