** Sometimes (i)CR may be claimed when subsequent scans suggest small lesions were likely still present and in fact the patient had (i)PR, not (i)CR at the first time point. Under these circumstances, the original (i)CR should be changed to (i)PR in the eCRF and the best response is (i)PR. If that is not the case, the (i)BOR of (i)SD will be determined considering two consecutive assessments better than (i)SD. This applies to both RECIST 1.1 and iRECIST.

- **Per PCWG3-modified RECIST 1.1:** the BOR derivation will be performed exactly as per RECIST 1.1, with the following exceptions: The derivation will be performed for all subjects, including those without measurable disease; Step 3 will be derived as BOR of Non-CR / Non-PD (instead of SD) for patients with non-measurable disease. Step 5 will consider first the possibility of PDu without any subsequent confirmation of PD, in this case, the BOR as per PCWG3-modified RECIST 1.1 will be PDu:

Step	Condition
Step 1: BOR of CR (measurable disease only) If a BOR of CR is not determined, Step 2 will be performed.	At least two consecutive determinations of CR more than 4 weeks apart, or if not consecutive, with no other assessment between the two determinations other than unable to evaluate (NE), CR.

Step	Condition

Step 2: BOR of PR (measurable disease only) If a BOR of PR is not determined, Step 3 will be performed.
	
At least two consecutive determinations of PR or CR, more than 4 weeks apart, or if not consecutive, with no other assessment between the two determinations other than NE, CR, PR.

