
If measurable disease: Step 3: BOR of SD If a BOR of SD is not determined, Step 4 will be performed. or If non-measurable disease: Step 3: BOR of Non-CR/Non-PD If a BOR of Non-CR/Non-PD is not determined, Step 4 will be performed.
	
At least one SD assessment (or better), \geq 6 weeks (\geq 42 days) after start of study treatment; if not, at least one follow-up scan (i.e., consecutive scan) evaluated as SD (or better) is required to determine a BOR of SD. If not consecutive scans, with no other assessment between the two determinations other than NE, CR, PR, SD.
 
At least one Non-CR/Non-PD assessment (or better), \geq 6 weeks (\geq 42 days) after start of study treatment; if not, at least one follow-up scan (i.e., consecutive scan) evaluated as Non-CR/Non-PD (or better) is required to determine a BOR of Non-CR/Non-PD. If not consecutive scans, with no other assessment between the two determinations other than NE, Non-CR/Non-PD.

Step 4: BOR of PD If a BOR of PD is not determined, Step 5 will be performed.
	
At least one (i.e., any) PD after baseline.

Step 5: BOR of PDu (non-measurable disease only) If a BOR of PDu is not determined, Step 6 will be performed.
	
At least one (i.e. any) PDu assessment after baseline.

Step 6: BOR of NED (non-measurable disease only) If a BOR of NED is not determined, Step 7 will be performed.
	
If no measurable disease at baseline and all subsequent assessments will be NED.

Step 7: BOR of NE
	
Measurable disease at baseline, but not all or any target lesions have been evaluated, or if derivation of BOR from Step 1 to 6 does not apply.

- **Per iRECIST:** The BOR according to iRECIST (iBOR) is defined as the best overall timepoint response recorded from the first dose date until confirmed disease progression, death, or start of new anti-cancer therapy, considering any requirement for confirmation. iBOR will be programmatically derived according to the following rules in a stepwise manner for patients with measurable disease only:

Step	Condition
Step 1: iBOR of iCR If an iBOR of iCR is not determined, Step 2 will be performed.	At least two consecutive determinations of iCR more than 4 weeks apart, or if not consecutive, with no other assessment between the two determinations other than unable to evaluate (NE), iCR.

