12.7.5 CBR and iCBR

CBR/iCBR will be summarized using descriptive statistics (frequency and percentage) together with a 95% CI for each indication separately.

CBR will be calculated based on PCWG3-modified RECIST for the mCRPC cohort separately for those patients with measurable disease at baseline and for all mCRPC patients.

Primarily, patients with missing data will be considered to be non-responders.

A sensitivity analysis will be performed for CBR and iCBR using the ASaT and Per Protocol populations; and without imputing for missing response.

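### In mCRPC, the PCWG3 BOR table contradicts its own text on unconfirmed bone progression, and the RECIST CBR and iCBR denominator is not stated (minor)

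*SAP*

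**What the plan says.** **Clinical benefit rate.** SAP 10.13.7 defines the RECIST 1.1 version: "The CBR is the proportion of patients who achieved BOR of CR, PR, or SD". The iCBR is the same with the iRECIST categories. Both rest on SAP 10.13.3, where "BOR will be determined according to the following rules in a stepwise manner for subjects with measurable disease"; the iBOR rules carry the same limit.

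SAP 12.7.5 restricts neither rate to measurable disease and adds: "Primarily, patients with missing data will be considered to be non-responders". It names denominators only for the PCWG3-modified CBR, which is reported once for measurable patients and once for all mCRPC patients. By contrast, SAP 12.7.1 restricts ORR to measurable disease and SAP 10.13.9 does so for time to response. The efficacy population (SAP 9.5) is defined by exposure, not by measurability. The Protocol section 3 endpoint table attaches a measurable-disease condition to ORR, BOR and time to response, but not to CBR.

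**Who is enrolled.** Protocol 5.1, criterion 5, says for mCRPC: "Patients with both measurable and non-measurable disease will be enrolled", and "At least 35 patients with measurable disease will be enrolled". SAP 8.1 plans 51 mCRPC patients.

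**PCWG3-modified BOR.** SAP 6.1 adds this analysis "to study the effect of progressive disease in bone on the BOR". The text introducing the table in SAP 10.13.3 applies it to all subjects and, for PDu that is never confirmed, says "in this case, the BOR as per PCWG3-modified RECIST 1.1 will be PDu". The table's own label begins "Step 5: BOR of PDu (non-measurable disease only". Step 7 sends whatever Steps 1 to 6 leave unresolved to NE.

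**The concern.** There are two separate specification gaps, both in mCRPC.

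1. **PDu.** The introductory text and the table give different answers for a measurable patient. SAP 10.13.2 maps any soft-tissue result other than PD, combined with bone PDu, to an overall PDu. A patient with stable soft tissue and an unconfirmed bone finding is therefore PDu under the text and NE under the table. In an analysis whose purpose is to show what bone disease does to BOR, NE reports a known finding as an absence of information.
2. **Denominator.** CBR and iCBR are built from a variable that does not exist for non-measurable patients, and the plan does not say whether those patients are counted. A programmer following 12.7.5 literally would count them as non-responders even when they are stable.

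At stake are the descriptive mCRPC figures for RECIST CBR and iCBR (secondary) and for PCWG3 BOR (sensitivity).

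**Working it through.** The documents give no target or expected value for CBR, iCBR or PCWG3 BOR, so there is no stated figure to reproduce. The nearest planned mCRPC figure is the futility rule (fewer than 1 response in 35, against a minimal ORR of 10.4%). With 0 of 35, the exact 80% upper limit is 1 − 0.1^(1/35) = 6.4%, below 10.4%. With 1 of 35 it is 10.7%, above 10.4%. The rule reproduces.

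**PDu.** The PCWG3 table was applied to measurable patients over every sequence of CR, PR, SD, PDu, PD and NE, stopping at PD, with and without the Step 5 restriction.

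| Scan weeks | Paths | BOR changes (NE under table, PDu under text) | CBR numerator changes |
|---|---|---|---|
| one scan (5.5 or 6) | 6 | 1 | 0 |
| 6, 12 | 36 | 3 | 0 |
| 5.5, 12 | 36 | 6 | 0 |
| 5.5, 12, 18 | 216 | 16 | 0 |

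These are counts of possible sequences, not probabilities. With scans at weeks 6 and 12, the three affected paths are PDu–PDu, PDu–NE and NE–PDu. A first scan before day 42 (week 5.5 is inside the ±2-week window) adds CR, PR or SD followed by PDu, because the early result alone does not meet Step 3. SD or better at day 42 or later still resolves at Step 3, and any PD resolves at Step 4. The CBR numerator never moves, because SAP 10.13.7 credits neither PDu nor NE.

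**Denominator.** Planned N = 51 and measurable m ≥ 35, so non-measurable patients number 51 − m, from 0 to 51 − 35 = 16. If they stay in the denominator and have no BOR, the highest attainable CBR is m/51.

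| Measurable m | Non-measurable | Ceiling m/51 |
|---|---|---|
| 35 | 16 | 68.6% |
| 40 | 11 | 78.4% |
| 45 | 6 | 88.2% |
| 51 | 0 | 100% |

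As an illustration at the worst case, assume 18 of 35 measurable patients benefit. Then 18/35 = 51.4% (exact 95% CI 34.0 to 68.6), against 18/51 = 35.3% (22.4 to 49.9). The 18 is an assumption.

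Running non-measurable patients through the RECIST table anyway would not rescue the stable ones. SAP 10.13.1 can return Non-CR/Non-PD, but no RECIST or iRECIST BOR step accepts the corresponding category, so a patient with that result throughout ends as NE. The NED step leads to a category that RECIST CBR does not credit. Only a confirmed complete disappearance of disease could then count.

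**The case against.** **On the denominator**, the best reply is that the intended meaning can be inferred. A rate defined on BOR arguably covers only those who have a BOR. SAP 6.1 presents the all-patient mCRPC CBR as a PCWG3 sensitivity analysis set against RECIST CBR, and SAP 10.13.7 treats measurable patients under PCWG3 as under RECIST 1.1. Both suggest that a measurable-only RECIST CBR was meant. The measurable-only PCWG3 CBR is a like-for-like comparator, and the all-patient version credits Non-CR/Non-PD and NED. A scanned patient for whom BOR is undefined is also not plainly a patient with missing data. This stands as evidence of intent. A reader might infer that the rules definitely make non-measurable patients failures; the documents do not go that far. But the intent is not written in 12.7.5, and iCBR has no all-patient counterpart.

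**On PDu**, the reply is that bone PD itself is still captured at Step 4, so only unconfirmed progression is mislabelled. That is correct and limits the reach. Three stronger readings are tempting and fail:

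- That NE in place of PDu makes CBR wrong. Neither category is benefit.
- That affected patients leave the no-imputation CBR and inflate it. SAP 12.7.5 does not define that analysis further. The only definition, in SAP 12.7.1 for ORR, keeps anyone with an evaluable post-baseline assessment, and PDu is a result distinct from NE.
- That all measurable patients, at least 35, are affected. Only those with PDu, nothing meeting Step 3 and no later PD are.

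**Conclusion.** Both points hold as drafting faults of minor severity, confined to secondary and sensitivity outputs in mCRPC.

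- **PDu:** text and table cannot both be followed. Under the table, some measurable patients with unconfirmed bone progression are reported as NE. How many is unknown.
- **Denominator:** it is unstated. On a literal reading, the RECIST CBR and iCBR ceiling is 68.6% at worst and 100% if every patient is measurable. This assumes that non-measurable patients are kept in the denominator, have no BOR and count as non-responders.

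The figures 51 and 35 are planned. SAP 6.1 reports that recruitment stopped after the August 2023 futility analysis, so the actual number and split are not known from these documents. A reader might infer that the primary result or the stopping decision is touched. It is not: ORR is restricted to measurable disease and uses RECIST 1.1 responses, and neither PDu nor NE is a response. The main CBR is likewise unaffected by the PDu fault.

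**What to change.** Make two SAP edits before database lock.

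1. In the PCWG3-modified BOR table of SAP 10.13.3, delete the bracketed restriction to non-measurable disease from Step 5, so that PDu applies to every mCRPC patient, as the introductory text says.
2. In SAP 12.7.5, state that RECIST CBR and iCBR in mCRPC use patients with measurable disease at baseline, as SAP 6.1 and 10.13.7 imply. Keep the PCWG3 CBR for all mCRPC patients as planned.

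The cost is two text changes and a small programming check. Some patients may move from NE to PDu in the PCWG3 BOR table. No new data are needed, and neither the primary analysis nor the futility rule has to be rerun.
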